9.6.3 Laboratory Test Results

Non-roll over subjects:

Clinical chemistry, hematology, and urinalysis data will be listed and reviewed for each subject. Values outside the normal laboratory reference ranges will be flagged as high or low on the listings.

The number and percentage of subjects experiencing treatment emergent laboratory toxicities with worst post dose CTCAE grades of ≥ 1 , ≥ 2 , ≥ 3 and 4 will be presented. The direction of the laboratory worsening will be denoted. The summary will be presented for all laboratory parameters for which at least one subject experienced a treatment emergent toxicity with a worst grade ≥ 3 .

Additionally, the number and percentage of subjects experiencing 1, 2, 3 and 4 worsening CTCAE grade shifts from baseline will be presented. The direction of the laboratory worsening will again be denoted.

Shifts tables indicating the change between the baseline and the maximum post dose CTCAE grades for an increased value, and the maximum post dose grade for a decreased value will be provided for selected laboratory parameters of interest.

A listing of CTCAE grade 3 or higher laboratory toxicities will be provided. This listing will include all laboratory data for the subject and laboratory parameter of interest in order to provide proper context. A flag will indicate the grade 3 or higher toxicity.

Summaries of the absolute value and/or changes from baseline at each scheduled assessment will be provided for selected laboratory parameters of interest.

A summary of the change from baseline to the post dose maximum, time to post-dose maximum, change from baseline to the post dose minimum, and the time to the post dose minimum may also be provided for selected parameters of interest.

Below is list of all lab tests performed for non-roll over subjects:

9.6.3.1 List of Analytes for Non-roll Over Subjects

Chemistry	Hematology	Urinalysis	Coagulation
Albumin	ANC	Blood	PT
ALP	Hematocrit	Protein	PTT
ALT	Hemoglobin	Ketones	INR
Amylase	Platelets	Bilirubin	
AST	RBCs	Glucose	Other Labs:
Bicarbonate	WBCs	Leucocytes esterase (WBC)	Pregnancy
BUN or Urea	Differential: 
▪ Neutrophils▪ Lymphocytes▪ Monocytes▪ Eosinophils▪ Basophils	Microscopic exam (only needed for positive dipstick and should include the following): 
Epithelial, Bacteria, Casts, Crystal, RBCs, WBCs	Hep B surface antigen
Calcium			Hep B antibody
Chloride			Hep C antibody
Creatinine			HCV PCR (if applicable)
Direct bilirubin			HBV PCR (if applicable)
Glucose			PK
LDH			Biomarker
Lipase			SPEP
Magnesium			UPEP
Phosphorus			sFLC
Potassium			Quantitative immunoglobulin
Sodium			Beta-2 microglobulin
Total bilirubin			Immunofixation
Total protein			
Uric acid			

Roll-over subjects:

Summary of clinical chemistry, hematology, urinalysis, and coagulation will be listed for each subject. Subjects laboratory parameters toxicities will be classified using CTCAE grade and their percentages will be tabulated. Summary CTCAE grade 3 and higher toxicities will be provided.

Below is list of all lab tests performed for roll-over subjects:

9.6.3.2 List of Analytes for Roll-over Subjects

Chemistry	Hematology	Urinalysis	Coagulation
Albumin	ANC	Blood	PT
ALP	Hematocrit	Protein	PTT
ALT	Hemoglobin	Ketones	INR
Amylase	Platelets	Bilirubin	
AST	RBCs	Glucose	Other Labs:
Bicarbonate	WBCs	Leucocytes esterase (WBC)	Pregnancy
BUN or Urea	Differential:	Microscopic exam (only needed for positive dipstick and should include the following):	Hep B surface antigen
Calcium	Neutrophils	Epithelial, Bacteria, Casts, Crystal, RBCs, WBCs	Hep B antibody
Chloride	Lymphocytes		Hep C antibody
Creatininine	Monocytes		HCV PCR (if applicable)
Direct bilirubin	Eosinophils		HBV PCR (if applicable)
Glucose	Basophils		PK
LDH			Biomarker
Lipase			SPEP
Magnesium			UPEP
Phosphorus			sFLC
Potassium			Quantitative immunoglobulin
Sodium			Beta-2 microglobulin
Total bilirubin			Immunofixation
Total protein			
Uric acid			

9.6.4 Vital Signs

Vital signs data will be listed and reviewed for each subject. Depending on the size and scope of changes, summaries of vital signs data over time and/or changes from baseline over time may be provided.

9.6.5 Physical Measurements

The change in weight from baseline to each scheduled assessment time point will be summarized.

9.6.6 Electrocardiogram

The electrocardiogram (ECG) measurements from this clinical study were performed as per standard of care for routine safety monitoring, rather than for purposes of assessment of potential QT interval corrected (QTc) effect. Because these evaluations may not necessarily be performed under the rigorous conditions expected to lead to meaningful evaluation of QTc data, these data would not be expected to be useful for meta-analysis with data from other trials.

9.6.7 Antibody Formation

NA

9.6.8 Exposure to Investigational Product

Descriptive statistics will be produced to describe the exposure to investigational product by treatment group.

9.6.9 Exposure to Other Protocol-required Therapy

Descriptive statistics will be produced to describe the exposure to each of the protocol specified treatment by treatment group.

9.6.10 Exposure to Concomitant Medication

The number and proportion of subjects receiving therapies of interest will be summarized by preferred term or category as coded by the World Health Organization Drug (WHO DRUG) dictionary.

9.7 Other Analyses

9.7.1 Analyses of Pharmacokinetic or Pharmacokinetic/
Endpoints

Non-roll over subjects:

The PK endpoints include, but are not limited to C_{max} , t_{max} , and AUC_{last} of oprozomib following dosing on cycle 1 day 8 and cycle 1 day 22.

Blood samples will be collected from all subjects for determination of plasma concentrations of oprozomib at time points specified in the schedule of assessments (Table 4 in the protocol). Individual oprozomib concentration-time data and summary statistics will be tabulated for each dose level. Individual, mean, and standard deviation concentration-time data may be plotted for each dose level.

PK parameters will be calculated using non-compartmental methods. Actual dosing and sampling times will be used for calculation of PK parameters. PK parameter estimates will be summarized descriptively. Other pharmacokinetic parameters such as AUC from time 0 to the time extrapolated to infinity (AUC_{inf}), apparent clearance (CL/F), and terminal half-life ($t_{1/2}$) may be analyzed. Population PK modeling may be performed to better characterize the PK of oprozomib using intense sampling following dosing on cycle 1 day 8 and cycle 1 day 22 and sparse sampling in day 1 of cycles 1, 3 and 5.

9.7.2 Analyses of Clinical Outcome Assessments

NA

9.7.3 Analyses of Health Economic Endpoints

NA

10. Changes From Protocol-specified Analyses

There are no changes to the protocol-specified analyses.

11. Literature Citations / References

12. Appendices

Appendix A. Technical Detail and Supplemental Information Regarding Statistical Procedures and Programs

Handling of Missing or Incomplete Dates for Adverse Events and Concomitant Medications

Imputation Rules for Partial or Missing Stop Dates

If the month and year are present, impute the last day of the month. If only the year is present, impute December 31 of that year. If the stop date is entirely missing, assume the event or medication is ongoing. If a partial or complete stop date is present and the 'ongoing' or 'continuing' box is checked, then it will be assumed that the AE or conmed stopped and the stop date will be imputed, if partial.

Imputation Rules for Partial or Missing Start Dates

		Stop Date						
		Complete: yyyymmdd		Partial: yyyymm		Partial: yyyy		Missing
Start Date		<1 st Dose	≥1 st Dose	<1 st Dose yyyymm	≥1 st Dose yyyymm	<1 st Dose yyyy	≥1 st Dose yyyy	
Partial: yyyymm	=1 st Dose yyyymm	2	1	2	1	N/A	1	1
	≥ 1 st Dose yyyymm		2		2	2	2	2
Partial: YYYY	=1 st Dose yyyy	3	1	3	1	N/A	1	1
	≥ 1 st Dose yyyy		3		3	3	3	3
Missing		4	1	4	1	4	1	1

1 = Impute the date of first dose

2 = Impute the first of the month

3 = Impute January 1 of the year

4 = Impute January 1 of the stop year

Note: For subjects who were never treated (first dose date is missing), partial start dates will be set to the first day of the partial month.

Note: If the start date imputation leads to a start date that is after the stop date, then do not impute the start date

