- **Patients who are alive without documented disease progression, and have withdrawn consent at the time of analysis will be censored at the date of the last disease assessment before withdrawal of consent.**
- **Patients who have started an anti-cancer therapy other than the study treatment prior to documentation of disease progression will be censored at the date of the last disease assessment prior to start of new therapy.**

Best Overall Response (BOR)

The best response that a subject achieved during study where the responses are ranked from best to worst as follows: stringent complete response [sCR], complete response [CR], very good partial response [VGPR], and partial response [PR], minimal response [MR], stable disease [SD] and progressive disease [PD] (all according to Revised International Myeloma Working Group Uniform Response Criteria [IMWG-URC])

Overall Response Rate (ORR)

Proportion of subjects with BOR of sCR, CR, VGPR or PR.

Duration of Grade II GI Toxicity

Duration of Grade II GI toxicity is defined as the number of days between the start date through to the subsequent end date of the Grade II GI toxicity, or where applicable date of censoring [end date of the Grade II GI toxicity or date of censoring – start date of the Grade II GI toxicity +1]. Subjects whose Grade II GI toxicity do not end while on study will be censored at the date when they are last on study. Subjects who do not experience Grade II GI toxicity will be excluded from the analysis of duration of Grade II GI toxicity. **The intermittent adverse events will be excluded from the analysis of duration of Grade II GI toxicity, and not to be counted as one ongoing adverse event.**

Duration of Grade III or above GI Toxicity

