7.2 Primary Analysis

Non-roll over subjects:

The main objectives of the primary analysis are to determine the MTD for each formulation of oprozomib in combination with pomalidomide and dexamethasone and further evaluate the safety, tolerability and efficacy of the OPomd combination in subjects with relapsed or refractory multiple myeloma. In addition, this analysis will be used to possibly recommend the most appropriate oprozomib dose and formulation to be tested in future clinical trials in an OPomd combination. The selection of the oprozomib

recommended dose and formulation will be based on all data from the escalation cohorts.

Safety and tolerability will be assessed through summaries of study drug administration, DLTs, adverse events, changes in selected laboratory analytes, vital signs, and physical findings by dose level. Means and standard deviations will be used to summarize the total dose for each component of study drug received. All summaries will be presented by the assigned dose level and for all subjects.

All adverse event data will be listed by study site, dose level, subject identification number, and study day. All adverse events will be summarized by preferred term, appropriate thesaurus levels, and CTCAE (Version 4.03) toxicity grade. In addition, all serious adverse events, including deaths, will be listed separately and summarized.

Efficacy analyses of ORR and BOR will be performed using both the efficacy and safety population as defined previously.

Roll-over subjects: the main objective of the primary analysis of roll-over subjects is to evaluate the safety profile for all subjects on continued oprozomib treatment. Safety profile will be presented through descriptive statistics of safety data (treatment-emergent serious adverse events, treatment-emergent adverse events).

The primary analysis will be based on subject data collected up to two months from the date of last subject enrollment. **All available data up to and including the data cutoff date will be cleaned and a locked database will be used in the analysis.**

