8.3 Handling of Missing and Incomplete Data

The following imputation for missing or incomplete data will be performed if required:

Incomplete adverse event and concomitant medication dates missing data will be imputed as described in [Appendix A](#). If imputed dates are used, then they will be identified as such in the final study report.

Laboratory measurements that are below the quantification limits will be considered equal to the lower limit of quantification for all analyses unless explicitly noted otherwise.

Non-pharmacokinetic measurements (eg, ██████ data) that are below the lower limit of quantification will be considered equal to half of the lower limit of quantification for all analyses unless specified otherwise.

PK concentrations that are below the quantification limits will be set to zero when engaging non-compartmental model to compute PK parameters.

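### SAP Appendix A imputes partial adverse-event stop dates with no upper bound, so a GI-toxicity duration can end after death, end of study or data cutoff and count as uncensored

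*SAP*

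**What the plan says.** SAP Section 8.3 brings adverse-event dates under the appendix rules: "Incomplete adverse event and concomitant medication dates missing data will be imputed as described in" Appendix A. For stop dates, Appendix A gives these rules:

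- Month and year known: "If the month and year are present, impute the last day of the month".
- Year only: "If only the year is present, impute December 31 of that year".
- Nothing known: "If the stop date is entirely missing, assume the event or medication is ongoing".
- Partial or complete stop date, but the ongoing box is also ticked: "then it will be assumed that the AE or conmed stopped and the stop date will be imputed, if partial".

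The one check on date order concerns start dates: "If the start date imputation leads to a start date that is after the stop date, then do not impute the start date". No comparable check applies to an imputed stop date.

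SAP Section 5 defines the duration of Grade II GI toxicity as end date (or censoring date) minus start date plus 1. For events that do not resolve it says: "Subjects whose Grade II GI toxicity do not end while on study will be censored at the date when they are last on study". The definition for Grade III or above has the same form and the same censoring rule.

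For the primary analysis, SAP Section 7.2 says: "All available data up to and including the data cutoff date will be cleaned". That limits which data are used. It does not limit the value of an imputed date.

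**The concern.** The two sections treat nearly the same record in different ways. If the stop date is wholly blank, the event is ongoing and Section 5 censors it at the date last on study. If the site has entered only the year, Appendix A declares the event stopped on 31 December, and the Section 5 formula then gives a completed duration running to that day, even if the subject died or left months before. The record with more information yields the less plausible value, and that value enters as an observed end.

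At stake are the two GI-duration analyses. GI toxicity is the main tolerability issue for this drug: Protocol Section 5.5.5 names nausea, vomiting and diarrhea as the most common events and reports Grade 3 or higher GI events in 13 of 39 OPomd subjects. A duration that runs past death or the data cutoff would be a visible error in a summary that readers will look at.

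**Working it through.** The documents give no figure of their own to reproduce here, so the check applies the stated rules to dates.

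**Inputs from the documents.** Imputed stop = last day of the month, or 31 December (SAP Appendix A). Duration = end − start + 1; unresolved events are censored at the date last on study (SAP Section 5). Data cutoff = 02 December 2019 (notes to Tables 1 and 2, Protocol Section 5.5.5).

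**Assumed for illustration.** The start dates and the last-on-study date below.

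**Step 1: largest overrun.** Let B be the bounding date (death, end of study or cutoff), and suppose the partial date names the month or year in which B falls. Overrun = imputed stop − B.

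- Month known, B on the 1st of a 31-day month: 31 − 1 = 30 days.
- Year only, B on 1 January: 365 − 1 = 364 days; leap year 366 − 1 = 365 days.
- With B spread evenly over a 365-day year, the mean overrun is about 15 days (month known) or 182 days (year only).

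**Step 2: at the data cutoff.** A stop of December 2019, or of 2019 alone, becomes 31 December 2019. Overrun = 31 − 2 = 29 days. The text of Protocol Section 5.5.5 calls 21 August 2020 the cutoff, whereas the table notes call it the snapshot date. The table-note date is used here.

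**Step 3: one event, different records.** Start 10 March 2019; death or last on study 15 April 2019.

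| Stop date as recorded | End used | Duration | Status |
|---|---|---|---|
| Blank (ongoing) | 15 April | 36 + 1 = 37 days | censored |
| April 2019 | 30 April | 51 + 1 = 52 days | counted as ended |
| 2019 | 31 December | 296 + 1 = 297 days | counted as ended |
| April 2019 or 2019, capped | 15 April | 37 days | censored |

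**Step 4: subject still active at cutoff.** Start 05 November 2019, stop recorded as December 2019. Uncapped: 05 November to 31 December = 56 + 1 = 57 days, ended. Capped at 02 December: 27 + 1 = 28 days, censored.

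**Step 5: could another rule catch it?** The treatment-emergent window in SAP Section 5 limits when an event starts, not when it stops. The Appendix A order check covers start dates only. No other section bounds an imputed stop date.

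**The case against.** The strongest reply is that Section 5 already deals with the overrun. An event whose imputed end lies after the subject's last day did not end while on study, so the analysis-specific rule censors it there. That reading is possible, but the SAP does not state it. It sits badly with Appendix A, which assumes such an event has stopped, even against a ticked ongoing box. It also leaves open subjects still on study at the primary-analysis cutoff, for whom the SAP does not define the last date on study.

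A second reply is that partial dates should be rare. The protocol asks for onset and resolution dates (Section 12.2.2.1), data are checked and queried (Section 15.3), and both analyses use a cleaned, locked database (SAP Sections 7.2 and 7.3). This stands as a limit on size: the working shows what the rule can do, not how often it will.

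Three stronger readings are tempting, and the documents do not support them:

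- A reader might infer that imputing to month end is itself the defect, because it can only lengthen a duration. It is a pre-stated convention, and a cap leaves it unchanged wherever the bound is not reached.
- A reader might infer that one year-end date would dominate a cohort's summary, since OPomd cohorts hold 4 to 10 subjects. No visible text says how GI durations are summarized, by which grouping or with which statistic, and parts of the analysis sections are redacted. A median would resist one long value.
- A reader might infer that the cap costs nothing. Adverse events are followed until they stabilize or reverse (Protocol Section 12.2.2.1), so a recorded resolution can be genuine even when its imputed date passes the bound.

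**Conclusion.** The point holds as a gap between Appendix A and Section 5. Applied as written, the stop-date rule can place the end of a GI toxicity after death, end of study or data cutoff and give a longer, uncensored duration than Section 5 would give the same event had it never ended. The possible overruns are those in steps 1 and 2, and they assume that the partial date names the month or year of the bound.

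The consequence is small. The affected analyses are descriptive; GI duration is defined in Section 5 but does not appear in the visible endpoint table or in the visible text of SAP Section 9. Treatment-emergent status rests on onset, so adverse-event incidence does not change. Neither document feeds imputed stop dates into DLT assessment, so DLT counts and the MTD do not change. The documents do not give the frequency of partial stop dates, so no expected effect can be calculated. This is a low-priority clarification that is worth making.

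**What to change.** Add to SAP Appendix A: an imputed stop date may not be later than the earliest of the date of death, the end-of-study date and the data cutoff date. Where the month-end or year-end rule would pass that bound, set the date to the bound and, in the GI-duration analyses, censor the event there, in line with Section 5. Apply this to imputed dates only, and leave complete recorded stop dates as they are.

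The cost is one sentence in the SAP and one line of derivation code. There is a small statistical cost: some events that the site recorded as resolved in the bounding month or year become censored, although some of them did end on study. A footnote giving the number of durations censored for this reason would let readers judge the effect.
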